The purpose of this study is to examine oxygen therapy utilization and assess its impact on clinical and economic outcomes of ILD patients. There are three aims for this project:

Aim 1: To describe initiation and use of oxygen therapy among patients with fibrotic ILD. The specific objectives for Aim 1 are to:

- Examine the incidence and prevalence of oxygen therapy among patients with fibrotic ILD
- Assess the time to first oxygen therapy among fibrotic ILD patients naive to oxygen therapy, and examine factors/variables associated with oxygen therapy initiation

Aim 2: To assess the impact of oxygen therapy on clinical outcomes among patients with fibrotic ILD. The specific objective for Aim 2 is to:

- Evaluate the impact of oxygen therapy initiation on clinical outcomes, including disease progression and mortality, among fibrotic ILD patients

Study design:

This is a non-interventional study of patients enrolled in a commercial, Medicaid, or Medicare plan, using existing administrative claims and electronic health record (EHR) data in Optum's Market Clarity Integrated Claims + Clinical database for the period of 01 October 2015 through 30 June 2022 (study period). The study period may be extended though latest data available at the time of study implementation to increase study sample.

Patients aged ≥ 18 years with newly diagnosed fibrosing ILD will be identified from 01 October 2016 through 30 June 2022 (patient identification period). Patients will be required to have 12 months of baseline continuous enrollment prior to fibrosing ILD diagnosis for collecting patient demographics and clinical characteristics. The pre-ILD baseline period will also be used to describe baseline prevalence of oxygen therapy use. To describe the initiation and use of oxygen therapy after first fibrosing ILD diagnosis (Aim 1), patients will be followed for a variable period from the fibrosing ILD diagnosis date until the earlier of disenrollment from the health plan, end of study period, or death. Oxygen therapy use will be described, and results will be stratified by underlying cause of fibrosis (e.g., IPF vs. non-IPF ILD). Factors associated with initiation of oxygen therapy will be assessed using multivariable methods.

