7.3 VARIABLES

Variables related to the study period will be defined as follows:

Aim 1

- **Fibrosing ILD diagnosis date**—The first ILD diagnosis date for patients with ≥ 2 fibrosing ILD diagnoses on different dates and within 365 days. The fibrosing ILD diagnosis date is the first day of follow-up observation time for Aim 1.
- **Pre-ILD baseline period**—The 12-month period prior to the fibrosing ILD diagnosis date.
- **Aim 1 follow-up period**—The variable period starting on the fibrosing ILD diagnosis date and continuing until the earliest of the following: disenrollment from the health plan, death, or end of the study period. The Aim 1 follow-up period will be used to assess Aim 1 outcomes.
 - **All-cause mortality**—Death will be used as a censoring event and is further defined in Section 7.3.3.1.

Aim 2

- **Index date**—For the oxygen therapy cohort, the first date following the fibrosing ILD diagnosis date with a claim with diagnosis for oxygen therapy; for the no oxygen therapy cohort, a date within the same continuous enrollment period as the fibrosing ILD diagnosis date that is similar to the matched oxygen therapy patient in time from fibrosing ILD to index date. The index date is the first day of follow-up observation time for Aim 2 and Further Aim.
- **Pre-index baseline period**—The 12-month period prior to the index date.
- **Aim 2 follow-up period**—The variable period starting on the index date until the earliest of the following: disenrollment from the health plan, death, or the end of the study period. Matched pairs will be given the same duration of follow-up. The Aim 2 follow-up period will be used to assess Aim 2 and Further Aim outcomes.
 - **All-cause mortality**—Death will be used as a censoring event and is further defined in Section 7.3.3.1.

An overview of the analytic study variables and the study periods for which each analytic variable will be reported is provided in Table 1. Additional variable information is provided in Sections 7.3.1 to 7.3.4.

Table 1. Analytic Variables by Data Source and Time Period

Characteristic	Data source		Aim 1 time period		Aim 2 time period	
	Claims*	EHR	Pre-ILD baseline	Follow-up	Pre-index baseline	Follow-up
Aim 1 outcomes						
Oxygen therapy (time to initiation, sustained oxygen therapy use)		X		X	X	
Aim 2 outcomes						
Disease progression	X	X				X
All-cause mortality	X					X
Hypoxemia	X	X	X		X	X
Acute exacerbations	X	X				X
Patient characteristics†						
Index year	X		X		X	

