7.3.1 Aim 1 Outcomes

7.3.1.1 Primary Outcomes

- **Oxygen Therapy**—Evidence of oxygen use will be captured in the pre-ILD baseline and Aim 1 follow-up periods based on the presence of ≥ 1 diagnosis (ICD-10-CM), procedure (HCPCS, CPT), or revenue code for oxygen therapy. Among patients with oxygen therapy in follow-up, the following aspects of oxygen therapy will be described:
 - **Time to oxygen therapy initiation**—The time in days from the fibrosing ILD diagnosis date to oxygen therapy initiation, among patients without evidence of oxygen therapy in the pre-ILD baseline period.
 - **Sustained oxygen therapy use**—Using claims, sustained oxygen therapy use will be defined among patients with at least 12 months of follow-up after the index date (oxygen initiation date), as a binary variable for the presence of ≥ 11 claims for oxygen therapy in a 12-month period. The following aspects of sustained oxygen therapy will be described:
 - **Time to sustained oxygen therapy use**—The time in days between the index date and the earliest date that defined the sustained oxygen therapy use.
 - **Sustained oxygen therapy use within the first 12 months of follow-up**—The number of patients with the evidence of sustained oxygen therapy use during the first 12 months of follow-up.
 - **Note:** As a sensitivity analysis, sustained oxygen therapy use will also be defined as ≥ 6 claims for oxygen therapy in a 12-month period and, based on the distribution of the count of claims among the population, as the 75th percentile of claims in a 12-month period.

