7.6.1.2 Kaplan-Meier Analysis

Kaplan-Meier (KM) analysis will be used to evaluate time to oxygen therapy initiation from the fibrosing ILD diagnosis date among patients without baseline oxygen therapy use. When KM analysis is conducted, results will include censored-adjusted percentage of patients who have the event of interest at pre-specified time periods of interest (e.g., 6 month, 9 months, 12 months). In addition, the median (and 25th and 75th percentile) time to event and the 95% confidence interval (CI) around the median (and 25th and 75th percentile) will be reported. Censoring will occur at the first of the following: disenrollment from the health plan, end of the study period, or death.

Graphs of the cumulative incidence functions (i.e., $1-S(t)$ where $S(t)$ is the survival function) will be presented along with the cumulative percentage of patients with oxygen therapy initiation following the fibrosing ILD diagnosis date. Methods may account for competing events (e.g., death as competing event for oxygen therapy initiation).

[figure not shown]

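### Time to sustained oxygen use is limited to patients with 12 months of follow-up after oxygen start, a condition on the future that this measure does not need

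*Combined protocol and SAP*

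**What the plan says.** Sustained use is listed among the Aim 1 primary outcomes in Section 7.3.1.1. The population is part of the definition, which applies only "among patients with at least 12 months of follow-up after the index date (oxygen initiation date"). The event is at least 11 "claims for oxygen therapy in a 12-month period. The following aspects of sustained oxygen therapy will be described". Two sub-items follow, and neither is given a population of its own:

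- time to sustained use: "The time in days between the index date and the earliest date that defined the sustained oxygen therapy use";
- sustained use in the first year: "The number of patients with the evidence of sustained oxygen therapy use during the first 12 months of follow-up".

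Section 7.3 has Aim 1 follow-up "continuing until the earliest of the following: disenrollment from the health plan, death, or end of the study period". Otherwise Aim 1 sets no minimum follow-up; the abstract says "patients will be followed for a variable period from the fibrosing ILD diagnosis date until the earlier of disenrollment". The abstract's variable list names time to sustained use without mentioning the 12-month condition.

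The sensitivity analyses in Section 7.3.1.1 change the claim threshold (6 claims, or the 75th percentile of claims) but not the follow-up condition. Section 7.6.1.2 specifies Kaplan-Meier analysis only for time to initiation, and adds: "Methods may account for competing events (e.g., death as competing event for oxygen therapy initiation"). The limitations in Section 7.8 do not mention the restriction.

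**The concern.** The clock for time to sustained use starts at oxygen initiation, but whether a patient is counted depends on the following year. Death, disenrollment or study end in that year removes the patient. Three consequences follow.

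- Observed events are thrown away. Eleven claims can accrue before month 12, so a patient may qualify, leave before the year is out, and not be counted.
- The result describes initiators who stayed alive, enrolled and observable for a year. Aim 1 asks about oxygen use in fibrotic ILD patients generally.
- Section 7.6.1.1 reports results by IPF and non-IPF. If early exit differs between them, the two figures come from differently selected subsets.

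The condition also does not remove the need for censoring. The qualifying 12-month period is not tied to the first year, so the event can fall after month 12, when follow-up again varies between patients. No censoring rule specific to this outcome is given.

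**Working it through.** The plan gives no calculation for this outcome, so there is no figure to reproduce. The documents give no rate of death or disenrollment after oxygen start. The hazards below are assumptions, taken as constant: death 0.2 to 0.6 per year and disenrollment 0.1 to 0.3 per year, combined h = 0.3 to 0.9 per year.

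**1. Share excluded through death or disenrollment within 12 months**, 1 − exp(−h):
- h = 0.3: 1 − exp(−0.3) = 25.9%
- h = 0.9: 1 − exp(−0.9) = 59.3%

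Exits at study end are not in these figures.

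**2. Share that reaches the threshold and is still excluded.** Suppose every initiator has one claim a month from oxygen start. The 11th claim then falls at month 10 and the 6th at month 5. The share leaving between claim k at month m and month 12 is exp(−h·m/12) − exp(−h).

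| Definition | h = 0.3 | h = 0.9 |
|---|---|---|
| 11 claims (m = 10) | exp(−0.25) − exp(−0.30) = 3.8% | exp(−0.75) − exp(−0.90) = 6.6% |
| 6 claims (m = 5) | exp(−0.125) − exp(−0.30) = 14.2% | exp(−0.375) − exp(−0.90) = 28.1% |

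For 11 claims this is 3.8/25.9 = 15% to 6.6/59.3 = 11% of those excluded, so most excluded patients had not yet qualified. With fewer monthly users the share falls; with more frequent claims it could rise.

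**3. Exits at study end.** The identification period, 01 October 2016 to 30 June 2022, has 2,099 days and ends with the study period. The last 12 months are 365/2,099 = 17.4% of that calendar time. Anyone starting oxygen then is ineligible unless the study period is extended. This is a share of time, not of patients.

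**4. Scale from the plan's own counts.** In Table 3 a 6-month post-index requirement takes 80,151 patients to 34,299, a loss of 45,852 (57.2%). This is only indicative: the index there is the first ILD diagnosis, EHR activity is also required, and the window is 6 months.

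**5. What the restricted proportion can say about all initiators.** If a proportion p is sustained among those kept and a share e is excluded, the all-initiator proportion lies between p(1 − e) and p(1 − e) + e. With p = 50% assumed:
- e = 10%: 45% to 55%
- e = 30%: 35% to 65%
- e = 57%: 21.5% to 78.5%

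**6. Direction.** An illustrative simulation used two equal severity strata, annual exit probabilities of 10% to 50%, and a 30% to 70% chance of continuing monthly claims while observed. From 20% to 35% were excluded, and 1.7% to 2.6% of initiators reached 11 claims and were still excluded. The restricted proportion was 45% to 55%, against a 12-month cumulative incidence of 32% to 40% with every exit treated as competing. Against the proportion of all initiators who would have continued if observed, the restricted figure went both ways: 45.3% against 49.9% when sicker patients used oxygen more persistently, and 54.5% against 49.9% when they used it less.

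**The case against.** The strongest defence concerns the binary measure. A count of claims in 12 months, and above all a percentile of such counts, needs equal windows. Requiring a full year is a common descriptive choice, and the plan states it openly. This stands: for the binary item only labelling and a count of exclusions are missing.

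A reader might infer that the planned figure overstates how many initiators become sustained users. The documents do not support that as a fact. They promise a number of patients within a stated subset, not a proportion of all initiators. The restricted figure will usually exceed a cumulative incidence in which exit competes, but it can lie on either side of what excluded patients would have shown. A reader might also take 26% to 59% as the size of the bias. It is the share excluded under assumed hazards, and it leaves out administrative exits at study end, which need not be informative.

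It can also be said that cumulative incidence mixes persistence with survival: a group with higher mortality shows less sustained use because patients die. That is true, and it argues for showing both quantities rather than replacing one.

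Finally, competing-event methods are permitted, and the table shells, which might show denominators, are not reproduced in the public document. But the permission is optional, its example is initiation, and it does not lift the condition in Section 7.3.1.1.

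**Conclusion.** The point holds for time to sustained use. The 12-month condition selects on events after oxygen start, discards some observed events, and is unnecessary for a measure that can be censored. Under the assumptions of monthly claims in all initiators and a constant combined hazard of 0.3 to 0.9 per year, about 4% to 7% of initiators would be dropped after qualifying, and 14% to 28% under the 6-claim definition. Neither the sensitivity analyses, the Kaplan-Meier section nor the limitations deal with it.

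The direction and size of any bias cannot be known from the documents, and distortion of the IPF and non-IPF figures is conditional on early exit differing between them. Nor is this immortal-time bias in a treatment comparison: the outcome is descriptive within Aim 1, and the time-to-initiation and Cox analyses do not use the restriction. The change should be made, but it does not put the rest of Aim 1 in doubt.

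**What to change.** In Sections 7.3.1.1 and 7.6.1:

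- Analyse time to sustained use in all patients who start oxygen, from oxygen start, as a cumulative incidence with death as a competing event and censoring at disenrollment and study end. Report it overall and by IPF and non-IPF, for the 11-claim and 6-claim definitions.
- State that death is a competing event for this outcome, since Section 7.3 treats it as a censoring event for Aim 1.
- Keep the binary 12-month measure, and the percentile-based version, labelled as conditional on 12 months of follow-up after oxygen start.
- Report how many initiators that condition excludes, by reason (death, disenrollment, study end) and by IPF and non-IPF.
- Add the restriction to the limitations in Section 7.8.

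The cost is one added analysis on claims and dates already in the planned extract. The drawback is that the cumulative incidence reflects both persistence and survival, so it should be presented alongside the conditional proportion.

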7.2 SETTING

7.2.1 Secondary data source selection

The study will use administrative claims and EHR data from Optum's Market Clarity Integrated Claims + Clinical database.

7.2.2 Study population: Aim 1

The analysis for Aim 1 will include patients newly diagnosed with fibrosing ILD during the patient identification period. Patients must meet the following selection criteria to be included in the study:

Inclusion Criteria

- ≥ 2 fibrosing ILD diagnoses in any position on different dates of service, within 365 days of each other, and in the same continuous enrollment period during the patient identification period. The ***fibrosing ILD diagnosis date*** will be defined as the date of the first fibrosing ILD diagnosis. The two fibrosing ILD diagnosis codes can be one of the following combinations:
 - 2 fibrosis codes
 - 1 fibrosis code & 1 ILD code that requires fibrosis code
- ≥ 18 years of age as of the fibrosing ILD diagnosis date
- Continuous enrollment with medical and pharmacy coverage for 12 months prior to the fibrosing ILD diagnosis date (***pre-ILD baseline period***)

Exclusion Criteria

- Fibrosing ILD diagnosis in the 12-month pre-ILD baseline period
- Unknown gender or geographic region

Cohort Assignment

Patients meeting initial selection criteria for Aim 1 will be assigned to cohorts based on known cause of fibrosis:

- **IPF**— ≥ 2 medical claims with diagnosis for IPF in any position during the study period
- **Non-IPF ILD**— < 2 medical claims with diagnosis for IPF during the study period

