7.3.5.3 Healthcare Utilization Characteristics

- **Provider specialty**—A count of unique days with a non-inpatient claim for treatment by provider specialty category (primary care physician [including general/family practice, internal medicine], pulmonology and rheumatology) will be reported.
- **Medication use**—ILD medication use will be captured at the class level, including administrations and prescription fills. The number of prescriptions fills within each class will also be calculated. Treatment categories will include corticosteroids (methylprednisone, prednisone, prednisolone), biologics, (abatacept, denosumab, etanercept, tocilizumab, infliximab, rituximab), calcineurin inhibitors (cyclosporine, tacrolimus), and other immunosuppressants (mycophenolate mofetil, hydroxychloroquine, leflunomide, methotrexate, sulfasalazine, chloroquine phosphate).
- **All-cause HCRU**—HCRU will be calculated for ambulatory visits (physician office and hospital outpatient), emergency department (ER) visits, inpatient admissions, and pharmacy fills.
- **All-cause health care costs**—Health care costs will be presented as standardized costs. Total costs will be calculated and presented in categories of pharmacy costs and medical costs (outpatient, inpatient, professional services). Costs will be adjusted using the annual medical care component of the Consumer Price Index (CPI) to reflect inflation between the date of the claim and the most recent year for which the annual CPI is available.

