7.4 DATA SOURCES

Figure 3. Optum Data Ecosystem

Optum's Clinical EHR Database aggregates extensive clinical encounter data from a network of 140,000+ providers at more than 700 hospitals and 7,000+ clinics. The Clinical EHR Database currently has more than 104 million unique patients across the United States, with an average of 45 months of observed data per patient.

The Clinical EHR Database is robust, longitudinally linked, compliant with the Health Information Portability and Accountability Act of 1996 (HIPAA), and statistically de-identified. Data elements include demographics; medications prescribed and administered; immunizations; allergies; lab results (including microbiology); vital signs and other observable measurements; clinical and inpatient stay administrative data; and coded diagnoses and procedures.

Optum's Clinical EHR Database can deliver a longitudinal record that covers a comprehensive spectrum of patient health, medical information, and treatment decisions.

Optum Market Clarity dataset

The Optum Market Clarity dataset includes de-identified, deterministically linked claims data integrated with Optum's Clinical EHR data. It is fully HIPAA-compliant and statistician-certified. Clinical data are combined with adjudicated medical and pharmacy claims from both Optum-affiliated and non-affiliated payers. The Market Clarity dataset links EHR data with historical, linked administrative claim data, pharmacy claims, physician claims, facility claims (with clinical information), medications prescribed and administered, diagnoses, procedures, and information derived from clinical notes using NLP. For this study, the subset of individuals with health plan enrollment data available will be used. Insurance coverage will include commercial, Medicaid, and Medicare.

Figure 4. Market Clarity Data**7.5 STUDY SIZE**

Using data for Market Clarity integrated claims and clinical EHR data from 01 Jan 2016 - 31 May 2022, 1,179,017 patients with fibrosing-ILD were identified. Among them, 34,299 adult patients had at least one claim for oxygen therapy with 6 months of continuous enrollment in claims and 6 months of continuous activity in EHR.

These counts are for informational purposes only and may not reflect the final sample size. Application of other inclusion and exclusion criteria required for this study or other factors may reduce the sample size.

Table 3. Feasibility Counts from Market Clarity

Criteria	N

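### Sustained oxygen use is defined by a count of claims and not by distinct months with oxygen, so clustered billing can meet the 11-claim rule well before 11 months of use

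*Combined protocol and SAP*

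**What the plan says.** Section 7.3.1.1 lists sustained oxygen use among the Aim 1 primary outcomes and defines it "as a binary variable for the presence of ≥ 11 claims for oxygen therapy in a 12-month period". Evidence of oxygen is captured "based on the presence of ≥ 1 diagnosis (ICD-10-CM), procedure (HCPCS, CPT), or revenue code for oxygen therapy". Only patients followed for at least 12 months after starting oxygen are assessed.

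Two quantities are then described. One is the number of patients with sustained use in the first 12 months. The other is the time to sustained use: "The time in days between the index date and the earliest date that defined the sustained oxygen therapy use". The abstract (Section 2.1.1) names both as Aim 1 outcomes.

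Two sensitivity definitions are planned. In one, "sustained oxygen therapy use will also be defined as ≥ 6 claims for oxygen therapy in a 12-month period". The other sets the cut-off at the 75th percentile of the number of claims in 12 months.

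The section does not say whether a claim is a header, a line or a service date. It does not ask for different dates or months, does not merge claims from one day or one hospital stay, and does not set inpatient claims aside. According to Section 7.4, the data source holds both physician and facility claims.

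**The concern.** A threshold of 11 in 12 months looks chosen to mean oxygen in nearly every month. It has that meaning only if each month of use produces one claim, which the protocol neither states nor enforces. If a month can carry several claims (for example equipment, a visit with an oxygen diagnosis code, or a facility charge), a few months of dense billing satisfy the rule.

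Both outcomes built on the rule are affected: the proportion with sustained use could rise, and the time to sustained use could fall, because of billing practice and not because of use. Differences between the IPF and non-IPF strata, or between payers, could then partly reflect how oxygen is billed.

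**Working it through.** **No figure to reproduce.** The documents give no sample size, event count or expected proportion for this outcome, and no number of oxygen claims per patient-month. The check is therefore a logical comparison of two rules, followed by counting arithmetic on assumed rates.

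**Step 1: direction.** Compare the 11-claim rule with a rule that asks for oxygen claims in 11 distinct months of the same window, each claim being assigned to one month by its service date.
- A patient with oxygen claims in 11 distinct months has at least one claim in each, so at least 11 claims. Everyone who meets the month rule meets the claim rule.
- The reverse fails: 11 claims can lie in one month or a few.
- For a patient who meets both, the eleventh claim cannot come after the earliest claim in the eleventh distinct month.

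So the claim rule classes the same number of patients as sustained or more. If time runs to the qualifying claim, it does so on the same day or earlier.

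**Step 2: timing under regular billing.** Inputs: the thresholds 11 and 6 (Section 7.3.1.1), and an assumed k claims billed together every 30 days from day 0. A threshold T is met after ceil(T/k) billing dates, that is on day 30 × (ceil(T/k) − 1). For T = 11 and k = 2: ceil(5.5) = 6, and 30 × 5 = day 150.

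| Assumed claims per month | Billing dates needed for 11 | Day 11 is met | Day 6 is met |
|---|---|---|---|
| 1 | 11 | 300 | 150 |
| 2 | 6 | 150 | 60 |
| 3 | 4 | 90 | 30 |
| 4 | 3 | 60 | 30 |

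Under the month rule the 11-month threshold is met on day 300 in every row.

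**Step 3: a hospital stay.** Assume s counted claims at day 0 and one claim every 30 days after that. The eleventh claim falls on day 30 × (11 − s): day 240 for s = 3, day 180 for s = 5, day 90 for s = 8, and day 0 for s = 11.

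**Step 4: do the sensitivity definitions detect clustering?** The 6-claim version keeps the unit and lowers the threshold, so it is met sooner in every row. The 75th-percentile version moves the cut-off with the general level of billing but still ranks patients by number of claims. Neither looks at how claims are spread over the year.

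**Step 5: comparison with other variables in the protocol.** For the ILD diagnosis, Section 7.2.2 asks for "≥ 2 fibrosing ILD diagnoses in any position on different dates of service, within 365 days of each other". For provider specialty, Section 7.3.5.3 reports "A count of unique days with a non-inpatient claim for treatment by provider specialty category". Section 7.3.3.2 merges exacerbations that occur within 14 days of one another. The sustained-use rule has no such provision.

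**The case against.** The strongest reply is that no harm has been shown. The documents contain no billing frequencies, so two or three claims per month are assumptions. If nearly all patients generate one claim per month, the two rules agree. Claims can also be missing or incomplete, as Section 7.8 acknowledges, and infrequent billing under-counts use. The net error against true oxygen use therefore cannot be signed. This stands: only the direction relative to a month-based rule is fixed, and its size is unknown.

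The 75th-percentile definition deserves credit. If multiple claims per month are common, its cut-off rises with them, so it partly adapts to billing intensity. It still cannot separate 11 claims in four months from 11 claims in eleven.

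The table shells and code lists (Annexes 3 and 4) are not reproduced. A narrow code list could remove much of the multiplicity, but a list of codes does not by itself set a spacing or de-duplication rule.

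The consequences are also limited. Sustained use is described, not tested: in the visible text, the Kaplan-Meier and Cox analyses (Sections 7.6.1.2 and 7.6.1.3) are specified for oxygen initiation. The 12-month follow-up requirement keeps out patients whose billing is dense shortly before an early death.

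A reader might infer that one hospital stay makes a patient a sustained user. The documents do not support that as a general statement. It happens only if the stay yields 11 or more counted claims or lines; if a stay is counted as one facility claim, it adds one.

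**Conclusion.** The point holds as a weakness in the definition of a descriptive Aim 1 outcome. As written, the rule measures the volume of billing, and sustained use is inferred from it. Compared with a rule based on distinct months, it can only class as many patients or more as sustained; that result needs no billing data.

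The size cannot be derived from the documents. On the assumed pattern, qualification moves from day 300 to day 150 at two claims per month and to day 90 at three. These days assume that time runs to the eleventh claim. The protocol does not say whether the defining date is the first or the last claim of the qualifying set. On the first-claim reading, with billing from the index date, the time would be zero at every billing rate and the day figures would not apply.

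It would go too far to infer that the proportion is known to be overstated against true use. Nor does the problem reach the Aim 2 comparison: exposure there needs only one oxygen claim (Sections 7.2.3 and 7.3.2) and does not use this variable.

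**What to change.** Define sustained use as oxygen evidence in at least 11 distinct calendar months, or 30-day intervals, of a 12-month window. Use at least 6 distinct months as the sensitivity rule. State the counting unit, how inpatient and emergency oxygen claims are handled, and whether the qualifying date belongs to the first or the last qualifying month. Keep the claim-count version as a further sensitivity analysis; the gap between it and the month-based result shows how much clustering matters in these data.

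The cost is a little more programming on data already to be extracted. The downside concerns patients billed quarterly, who have about 4 billing dates a year (5 at most on a 90-day cycle from day 0: days 0, 90, 180, 270 and 360). They would fail both month rules. With one claim per bill they already fail the present 11- and 6-claim rules, so nothing is lost for them. With three claims per bill they would have 4 × 3 = 12 claims, qualify now, and cease to qualify. Reporting how many patients have regular bills about 90 days apart would show whether this matters.
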